2.1 Trial objectives

The **primary objective** is:

- To describe the robustness of data on HRV data obtained by two different monitoring systems in daily care of critically ill patients. The Isansys wireless monitoring device will be compared to the gold-standard holter monitoring device for ECG analysis.

The **secondary objectives** are:

- To identify the most suitable and cost-efficient device for HRV monitoring in critically ill patients.
- To define amendments in data capture and analysis required to proceed to a larger clinical trial
- To generate preliminary data on the variation of HRV in a critical care patients.

Primary outcome:

- Number of interpretable monitoring epochs in each HRV monitoring system after elimination of artefacts, extra beats and interference

Secondary outcomes:

- Correlation and comparison of HRV time, frequency and non-linear measures between the Isansys monitoring device and the gold-standard holter monitoring system.
- Correlation between HRV and onset of arrhythmias (ventricular or atrial)
- Correlation between HRV and cardiorespiratory events that commonly occur in critically ill patients, including, oxygen desaturation (SaO₂<85%), variations in blood pressure of >20%, change in ventilatory support, muscle paralysis, position of the patient, administration of vasopressors (e.g. noradrenaline and vasopressin).
- Nurses' and medical staff's perception of the usability of both monitoring systems in daily routine

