Whilst both monitoring devices are capable of recording continuous ECG and HRV data, it remains unclear how robust the data are with regards to interference and artefacts. In particular, it is unclear how each monitoring device will operate whilst patients are undergoing daily care maneuvers such as physiotherapy, washing and patient repositioning. Furthermore, it has not been described yet how HRV is affected by interventions such as mechanical ventilation, administration of inotropes or vasopressors, paralysis agents, or renal replacement therapy. The current study aims to elucidate the impact of these standard interventions on HRV and the robustness of HRV measurement between the Isansys wireless monitor and the gold-standard HRV monitoring technique. This feasibility study will aide decision making with regard to which device will be most suitable for further studies of HRV in critically unwell patients.

2. Trial Objectives, Design and Statistics

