2.3 Trial Statistics

ECG data will be downloaded from the holter device and analysis in holter device software package which derive HRV data. RR interval data from the Isansys patch will be downloaded onto an Excel spreadsheet. The RR interval will be uploaded to Matlab. The Medical Engineering and Clinical Physics department have developed a program in the Matlab environment for analysis and output of HRV data. ECG data will undergo preprocessing to remove artefacts and ectopic beats and be analysed using the Ornstein-Uhlenbeck third-order Gaussian process applied to the heart rate/RR interval.¹¹ This technique has been developed by the Medical Engineering and Clinical Physics department. Once the ECG has been preprocessed heart rate variability will be derived according to the European Society of Cardiology guidelines.²

We will use time domain measures, frequency domain measures and non-linear measures such as the poincare plot, approximate and sample entropy and detrended fluctuation analysis in our analysis of HRV.

Comparison between devices will be assessed by Bland-Altman methodology. The difference between measures recorded from the Holter monitor and the Isansys wireless monitor will be plotted against the average value for each HRV measure for individual patients. Any measure of relationship between the measurement error and the estimate of the true value (average of the two measurements) can be examined. If the difference between the Isansys monitor and the holter monitor is sufficiently small not to cause problems in the clinical interpretation (within 95% limits of agreement), then the Isansys wireless device can be considered to be interchangeable with the gold-standard holter monitoring device.

Heart rate variability data will be analysed statistically as described. Descriptive statistics showing means \pm standard deviation (SD) for continuously distributed variables, and number and proportions for categorical variables will be used for all comparisons. Chi-square tests will be used for categorical outcomes unless assumptions of the test are found to have been violated, in which case Fisher's exact test will be used.

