4.3 Schedule of study procedure

With informed consent, the following routinely recorded clinical and laboratory data will be collected:

- Baseline demographics and comorbidities
- Administration of beta blockers or anti-arrhythmics
- Administration of sedative agents (general anaesthetics/opioids/benzodiazepines)
- Reasons for admission to ICU
- Daily biochemistry and haematology results
- Severity of illness scores, including APACHE II and daily SOFA scores
- Daily CAM ICU scores / delirium
- Daily cardiac rhythm as per nursing entry or clinical diagnosis
- Daily clinical parameters, including medications (vasopressors/ionotropes/steroids/muscle relaxants) and organ support
- Daily AKI stage, including treatment with RRT

After obtaining informed consent, continuous ECG data will be recorded using the two different devices. ECG data will then be processed to derive HRV using the methodology described by the European Society of Cardiology Taskforce guidelines.² Processing of ECG data entails checking

for and removal of extrasystole and ectopic beats with interpolation of QRS complexes as described elsewhere.² Continuous 24 hour ECG recording will then be divided into 5 minute epochs for which short term HRV values will be calculated. HRV will be calculated in the time domain, frequency domain and non-linear domains for each 5 minute epoch. Entire 24 hour ECG recordings will be used for long term HRV measures in the time domain, frequency domain and non-linear domains as described the Taskforce guidelines.² HRV data will then be analysed according to that described in the statistical methodology and analysis section. HRV data will be calculated by the Medical Engineering and Clinical Physics department at the Royal Liverpool and Broadgreen University Hospital. They will be blinded to any patient identifiable or clinical information.

Daily data will be collected until day 5 in ICU, day of discharge from ICU or day of death (depending on what occurs first). In addition, we will record ICU and hospital length of stay, ICU and hospital mortality and occurrence of arrhythmias during ICU stay, after 30 days, and after 90 days following enrollment. Data will be collected by accessing routinely available results in the patients' medical records, and if necessary, by contacting the patient's General Practitioner (GP).

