6.2 Safety of Heart rate variability monitoring devices

Device 1

Isansys Lifetouch Sensor is a fully CE marked medical device. The monitoring system includes single use wearable adhesive patches which are supplied in at least three sizes, depending on the age and size of the patient. Each Lifetouch provides the following clinical data continuously for a period of up to 5 days:

- Heart rate
- Respiration rate
- Real time heart rate variability
- Visualization of the ECG
- 3 axes accelerometer output

The Isansys Lifetouch Sensor is fully wireless and battery operated. The battery is not accessible to the patient or staff. All Isansys Lifetouch Sensor are single patient use and will be disposed off by following local procedures Information is transmitted wirelessly to a mobile patient status engine (ipad) via wifi and Low energy Bluetooth connectivity. The patient status engine Gateway is supplied in a protective medical grade bezel frame sealed in such a way to allow it to be cleaned with standard disinfecting/sterilising liquids or wipes. The device is safe with all other intensive care monitoring.

Device 2

Ambulatory Holter ECG monitoring is a standard of care used by the cardiorespiratory department. Ambulatory holter monitoring involves attaching a 12 lead ECG to the patient in the standard ECG lead configuration using standard ECG adhesive dots. Holter monitors record continuously for 72 hours onto a memory card and are entirely battery operated with no new electrical connection to the patient. Following 72 hours the memory card is analysed using software provided by the holter monitoring company. The software is of medical standard and provides HRV data, data on the number of interpretable episodes, data on ectopic beats and arrhythmias. Ambulatory holter monitoring is already in routine clinical use within the Royal Liverpool and Broadgreen University Hospital. They are CE marked and validate for use on patients.

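### The single count of interpretable epochs per device cannot show performance during care manoeuvres, and the data named for collection would not allow a later split

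*Protocol*

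**What the plan says.** Protocol 2.1 gives the primary objective as "To describe the robustness of data on HRV data obtained by two different monitoring systems in daily care of critically ill patients". The synopsis has nearly the same wording. The last paragraph of the Introduction says what is not yet known: "it is unclear how each monitoring device will operate whilst patients are undergoing daily care maneuvers such as physiotherapy, washing and patient repositioning".

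The primary outcome in 2.1 is "Number of interpretable monitoring epochs in each HRV monitoring system after elimination of artefacts, extra beats and interference". Neither 2.1 nor the synopsis divides this count by activity, movement or rest.

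On data, 2.3 states that "RR interval data from the Isansys patch will be downloaded onto an Excel spreadsheet" and names no other patch output; the synopsis says the same. Section 4.3 lists clinical data that are mostly daily, and none of them is a time of washing, physiotherapy or turning. Patient position appears in 2.1 only within a secondary outcome, as something to correlate with HRV values, and 4.3 lists no item that would capture it.

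Section 6.2 says of the patch: "Each Lifetouch provides the following clinical data continuously for a period of up to 5 days". The list that follows includes "3 axes accelerometer output". For the Holter, "Holter monitors record continuously for 72 hours onto a memory card". Section 4.3 sets the unit of analysis: "Continuous 24 hour ECG recording will then be divided into 5 minute epochs".

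**The concern.** The Introduction asks how each device copes when the patient is being handled. A single total mixes those periods with all the other hours of recording. If care takes up a small part of the day, a large difference between the devices during care makes up only a small part of the total. Two devices that behave very differently during washing or turning could then have similar totals, and the total would not show where epochs were lost.

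The gap lies in the data as well as in the analysis. A stratified table can be added in an SAP, but only if something recorded during the study separates care or movement from rest. Neither the patch download described nor the clinical list does so. The study is meant to guide the choice of device for later HRV research and to define changes in data capture for a larger trial, so knowing where a device fails is part of its purpose.

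**Working it through.** The plan states no figure for this point, so there is nothing to reproduce. The check is how much of a difference during care survives pooling.

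**Inputs from the Protocol**
- Epoch length 5 minutes (4.3), so 12 epochs per hour.
- Holter recording 72 h and patch up to 5 days (6.2), so the longest shared window is 72 h: 72 × 12 = 864 epochs.

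**Assumed inputs (not in the Protocol)**
- Care time of 1, 2 or 4 h per 24 h, so the share of time in care, w, is 1/24, 2/24 or 4/24.
- Loss of epochs at rest: 1% on both devices.
- Loss of epochs during care: 50% on one device, 10% on the other.

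**Formula**

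Overall loss = w × (loss in care) + (1 − w) × (loss at rest).

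Pooled gap = w × (gap in care) + (1 − w) × (gap at rest). With equal performance at rest the second term is zero, and the pooled gap is w × (gap in care).

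**Results**

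| Care per day | Care epochs of 864 | Overall loss, device A | Overall loss, device B | Pooled gap |
|---|---|---|---|---|
| 1 h | 36 | 3.0% | 1.4% | 40 × 1/24 = 1.7 points |
| 2 h | 72 | 5.1% | 1.8% | 40 × 2/24 = 3.3 points |
| 4 h | 144 | 9.2% | 2.5% | 40 × 4/24 = 6.7 points |

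For example, at 2 h device A loses 2/24 × 50% + 22/24 × 1% = 5.1%, and device B loses 2/24 × 10% + 22/24 × 1% = 1.8%.

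**Sensitivity to the assumptions**
- A different set (95% interpretable at rest on both devices; 80% v 40% during care) has the same 40-point gap in care and gives the same 1.7, 3.3 and 6.7 points. At 6 h of care per day it gives 40 × 6/24 = 10.0 points. The level at rest does not matter as long as it is the same for both devices.
- If the levels at rest differ, the total can hide the gap. With the patch at 97% and the Holter at 93% at rest, and 40% v 80% in care, at 2 h the pooled gap (patch minus Holter) is 22/24 × 4 − 2/24 × 40 = +0.3 points, despite a 40-point deficit of the patch in care.

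**The case against.** **The objective can be read more broadly.** Daily care may simply mean routine ICU conditions at all hours. On that reading total yield answers the question and also helps to choose a device. This stands: the pooled count is valid and should be kept. It is incomplete only for the uncertainty that the Introduction singles out.

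**The size is assumed.** The Protocol gives neither care hours nor loss rates. It requires ventilation but not sedation, provides for patients with capacity (4.2) and collects delirium scores (4.3). The Introduction says that ECG recording in the critically ill is often disturbed, without limiting this to care. So a quiet patient with 1% loss at rest has no support in the document. This also stands. The multiplication by the share of time in care needs only equal performance at rest, but the particular figures are illustrations.

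**Two stronger readings are tempting.** A reader might infer that the study could declare the devices equally robust. The Protocol sets no test or margin for the epoch count, and the interchangeability statement in 2.3 concerns the HRV measures. Nor would the example disappear in a reported count: at 2 h of care, 864 × 5.1% is about 44 lost epochs against 864 × 1.8%, about 15. What the count would not show is when they were lost. A reader might also infer that the accelerometer trace is thrown away. Section 2.3 describes the HRV pipeline and names RR data only; it does not say that other outputs are discarded.

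**An accelerometer split has its own weakness.** The label comes from one of the two devices compared. If the patch detaches or loses its link during turning, RR and accelerometer data may vanish together, and its worst failures would leave the movement stratum. This is correct, and the fix has to deal with it.

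**Stratified tables are SAP content.** That is true of the table, but not of whether the data to build it are collected.

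**Conclusion.** The point holds in a limited form. The primary count describes overall yield but cannot show how each device performs during the manoeuvres that the Introduction names, and the data named in 2.3 and 4.3 would not allow a later split. When the devices perform equally at rest, the pooled gap is the gap in care multiplied by the share of time in care. On the assumed inputs that is about one twenty-fourth to one sixth of it for 1 to 4 h per day. Unequal performance at rest can shrink or mask it further. The relation is exact; the sizes depend on care hours and loss rates that the Protocol does not give.

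The documents do not support saying that the primary outcome is invalid, that the study would wrongly conclude equality, or that accelerometer data will be lost. This is a worthwhile improvement to a pilot study, best made before recording starts.

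**What to change.** Keep the overall count as it is and add the following.

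1. Export the patch's accelerometer output together with the RR intervals.
2. Align the patch and Holter clocks, so that both devices are judged on the same 5-minute epochs.
3. Label each shared epoch as movement or rest by a threshold fixed before the devices are compared.
4. Report interpretable epochs over epochs scheduled, per device, in three strata: movement, rest, and no accelerometer signal. Count epochs in the third stratum as patch failures, so that patch dropout stays in the comparison.
5. Where nursing records already give times of washing, physiotherapy or turning, use them to check the label.

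This needs no new sensor and no bedside procedure. It is not free: it takes one more export, the clock alignment and a stratified table, and the Protocol describes neither an accelerometer export format nor any clock alignment. Movement is only a proxy for care, so the strata should be reported as movement and rest, not as care and no care.

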Descriptive statistics showing means \pm standard deviation (SD) for continuously distributed variables, and number and proportions for categorical variables will be used for all comparisons. Chi-square tests will be used for categorical outcomes unless assumptions of the test are found to have been violated, in which case Fisher's exact test will be used.

Parametric and nonparametric methods, as determined by the distribution of each variable, will be used to test statistical significance of continuous variables. Logistic regression will be utilized to assess the predictive value of HRV different outcomes (onset of arrhythmias, change in ventilatory setting, drop in blood pressure, desaturation) adjusting for covariates. Bland-altmann methodology will be used to assess the comparability of results between each HRV monitoring device (Isansys and Holter monitor).

Abbreviations used in study protocol

AF	Atrial Fibrillation
CRF	case report form
CRP	C-reactive protein
ECMO	extracorporeal membrane oxygenation
GCP	Good Clinical Practice
GP	General Practitioner
HRV	Heart Rate Variability
HF	High Frequency Domain
IQR	Interquartile Range
ICU	intensive care unit
LOS	Length of stay
LV	Left ventricle
LA	Left atrium
LF	Low frequency domain
LF/HR	Low frequency/High Frequency ratio
NN	Normal-Normal Interval
pNN50	Percentage of RR intervals that differ by greater than 50ms
RCT	randomized controlled trial
REC	Research Ethics Committee
RR	R-R Interval
RMSSD	Root mean square of successive RR intervals
SAPS	Simplified Acute Physiology Score
S	Area of ellipse of Poincare plot which represents total HRV
SD	standard deviation
SD1	Poincare plot standard deviation perpendicular to the line of identity
SD2	Poincare plot standard deviation along the line of identity
SD1/SD2	Ratio of SD1 to SD2
SDNN	Standard Deviation of NN interval
SDANN	Standard deviation of the average NN interval
VLF	Very low frequency domain
ULF	Ultra low frequency domain

Glossary of Research Terms and Abbreviations

AE	Adverse Event
AR	Adverse Reaction
ASR	Annual Safety Report
CA	Competent Authority
CI	Chief Investigator
CRF	Case Report Form
CRO	Contract Research Organisation
DMC	Data Monitoring Committee
ICF	Informed Consent Form
Main REC	Main Research Ethics Committee
NHS R&D	National Health Service Research & Development
PI	Principle Investigator
QA	Quality Assurance
Participant	An individual who takes part in a clinical trial
RCT	Randomised Controlled Trial
REC	Research Ethics Committee

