Parametric and nonparametric methods, as determined by the distribution of each variable, will be used to test statistical significance of continuous variables. Logistic regression will be utilized to assess the predictive value of HRV for different outcomes (mortality, ventilator free-days, length of stay, SOFA score) adjusting for covariates.

3. Sample Size, Selection and Withdrawal of Subjects

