3.1 Sample size

In this single-centre study we wish to analyse 40 consecutive patients in whom a complete set of data can be obtained. From our previous experiences the incidence of AF in our intensive care unit is approximately 13.8%. Therefore in a sample size of 40 patients we would expect 2-3 patients to develop AF. This would allow us the opportunity to investigate any correlation between the changes in HRV preceding the onset of AF and investigate our secondary objectives to inform a larger clinical trial.

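### Ectopic beats are removed and interpolated before HRV is related to arrhythmia onset, but the ectopic data already available from the Holter have no stated role, so a change in ectopy could be mistaken for an HRV precursor

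*Protocol*

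**What the plan says.** - **Outcome.** Protocol 2.1 sets the secondary outcome "Correlation between HRV and onset of arrhythmias (ventricular or atrial". Section 3.1 says what it is for: the sample should allow the team to "investigate any correlation between the changes in HRV preceding the onset of AF".
- **Cleaning.** Section 2.3 states that "ECG data will undergo preprocessing to remove artefacts and ectopic beats". Section 4.3 describes "removal of extrasystole and ectopic beats with interpolation of QRS complexes as described elsewhere", after which the recording is cut into 5-minute epochs.
- **Model.** The synopsis says "Logistic regression will be utilized to assess the predictive value of HRV different outcomes (onset of arrhythmias, change in ventilatory setting", with adjustment for covariates that it does not name. The matching sentence in 2.3 lists other outcomes, "mortality, ventilator free-days, length of stay, SOFA score) adjusting for covariates", and does not mention arrhythmia onset.
- **Ectopic data.** Section 6.2 says that the Holter software "provides HRV data, data on the number of interpretable episodes, data on ectopic beats and arrhythmias". No section names ectopic burden as a predictor, covariate, epoch filter, descriptor or sensitivity analysis for the arrhythmia outcome, and the list of collected data in 4.3 does not include it.

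**The concern.** Ectopic beats affect the HRV measures however they are handled. A premature beat that the cleaning misses adds large successive differences and raises RMSSD, pNN50, HF power and SD1. One that is caught and interpolated is replaced by a smoothed value and lowers them. After cleaning, short-term HRV therefore still depends partly on how much ectopy there was and how well it was caught.

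This matters most for the arrhythmia outcome. If ectopy changes in the period before onset, HRV can change with it while autonomic variability stays the same. Section 3.1 wants to read changes in HRV before AF and carry them into a larger trial. With only a handful of AF cases, one or two patients could settle the result. Without the ectopic burden alongside, a reader cannot tell which of the two is being seen.

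**Working it through.** **Inputs from the protocol.** 5-minute epochs (4.3); RMSSD as the root of the mean squared successive differences (Introduction); AF incidence 13.8%, 40 patients, 2 to 3 expected AF cases (3.1); 30 patients (synopsis, 4.5); 72-hour Holter recording (Introduction, 6.2).

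**Assumed inputs, not in the protocol.** Heart rate 90 bpm; baseline RMSSD 10, 20 or 40 ms; premature beat 35% early; 10 ectopics per epoch before onset against 2 otherwise; 90 to 95% of ectopics caught.

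**Step 1: the plan's own figure.** 40 × 0.138 = 5.5 expected AF cases and 30 × 0.138 = 4.1. The stated 2 to 3 does not follow from 13.8% of 40. That is a separate matter; here it only shows that the cases are few on any reading.

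**Step 2: one missed beat.** Mean RR = 60,000/90 = 667 ms, so an epoch holds 300/0.667 = 450 beats. The beat is early by d = 0.35 × 667 = 233 ms. With no pause the successive differences are −d, +d, which add 2d². With a full compensatory pause they are −d, +2d, −d, which add 6d². For k missed beats and c = 2 or 6:

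RMSSD = √(baseline² + c·k·d²/450), with 2d²/450 = 242 and 6d²/450 = 726.

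| Baseline RMSSD | One missed beat, no pause | One missed beat, full pause |
|---|---|---|
| 10 ms | 18.5 ms (1.85-fold) | 28.7 ms (2.87-fold) |
| 20 ms | √(400 + 242) = 25.3 ms (+27%) | √(400 + 726) = 33.6 ms (+68%) |
| 40 ms | 42.9 ms (+7%) | 48.2 ms (+21%) |

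SD1 equals RMSSD/√2 to a close approximation, so it moves in proportion. pNN50 gains 2 or 3 differences in 450, which is 0.4 or 0.7 percentage points. HF power rises in the same direction; its size was not calculated.

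**Step 3: epochs before onset against other epochs.** At 95% detection, 0.5 beats are missed on average before onset and 0.1 otherwise; at 90%, 1.0 and 0.2. The ratio of the two RMSSD values, from leakage alone, is:

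| Baseline RMSSD | No pause | Full pause |
|---|---|---|
| 10 ms | 1.33 to 1.52 | 1.64 to 1.84 |
| 20 ms | 1.11 to 1.20 | 1.27 to 1.44 |
| 40 ms | 1.03 to 1.06 | 1.08 to 1.15 |

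If ectopy is the same before onset as otherwise, the ratio is 1.

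**Step 4: the opposite direction.** A simulation used 450 independent intervals around 667 ms with true RMSSD 20 ms, and replaced each ectopic's interval and the next by linear interpolation. It gives 20.0 ms with no ectopics, 19.7 ms at 1% of beats, 18.7 ms at 5% and 17.3 ms at 10%. At 5% (22 beats) that is (19.99 − 18.66)/22 = 0.06 ms per ectopic. The contrast of 10 against 2 ectopics would then lower RMSSD by about 8 × 0.06 = 0.5 ms, or 2 to 3%. At these assumed rates leakage outweighs interpolation. With near-perfect detection or much heavier ectopy the net shift could be downward.

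**The case against.** The strongest reply is that this is an argument from silence. The synopsis promises adjustment for covariates in the arrhythmia model and names none, so ectopic burden is neither included nor ruled out. Covariate lists and sensitivity analyses are commonly left to a statistical analysis plan, which is not at hand. That stands against any claim that the ectopic count will go unused. It does not remove the point. The protocol itself fixes the removal step and the inference sought, and then gives no role to an output that it says exists. With so few AF cases, covariate adjustment could do little in any event.

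Other parts of the reply also stand:

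- A reader might infer that a false HRV signal *will* be reported. The documents give no miss rate and no trend in ectopy before onset, so *could* is the most they support.
- A reader might infer that, since only RR intervals are named for download from the patch in 2.3, ectopics there must be recognised by timing alone. But 2.3 also speaks of preprocessing ECG data, and the Introduction says that the patch's ECG is transmitted and stored. The Holter records 12 leads. One assumed detection rate for both devices is a simplification.
- A reader might want ectopic-free epochs as the main analysis, or require any relation to survive adjustment for ectopy. With so few cases the first could discard most of the data before onset. If ectopy lies on the path from autonomic change to AF, the second would over-adjust.
- The outcome is secondary, in a pilot feasibility study, and no decision rule rests on it.

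**Conclusion.** The point holds in a limited form. The protocol removes and interpolates ectopics, relates what remains to arrhythmia onset, and states no use of the Holter's ectopic data for that purpose. As written, it cannot separate an HRV precursor from a change in ectopy.

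The possible size runs from trivial to large. Under the assumed contrast in ectopy, leakage alone would make RMSSD before onset 3 to 15% higher at a baseline of 40 ms, 11 to 44% at 20 ms and 33 to 84% at 10 ms; interpolation pulls the other way. All of this rests on assumed heart rate, prematurity, ectopy, detection and baseline RMSSD, and the effect vanishes if ectopy does not change before onset. The defect is worth correcting because the remedy is cheap and the protocol aims to define improvements in data capture and analysis for a larger trial. It does not touch the primary outcome or invalidate the study.

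**What to change.** In Protocol 2.3, for the period covered by the Holter recording:

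1. Retain for each 5-minute epoch the Holter ectopic count, or the proportion of beats removed or interpolated.
2. Show it beside HRV in the epochs before each arrhythmia onset. For the few AF cases a plot per patient is enough.
3. Keep the planned all-epoch analysis as the main one, and repeat it in epochs with no or few flagged ectopics as a sensitivity analysis, with the threshold fixed beforehand.
4. Describe an HRV-arrhythmia relation as independent of ectopy only if it is also seen in the restricted analysis.

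Cost: a little extra analysis. Section 6.2 promises ectopic data but does not say that they come per epoch, so the export format should be checked before recruitment. The restricted analysis will contain few epochs before onset, and its result should be read as descriptive. Section 4.3 records arrhythmias throughout the ICU stay and beyond, so onsets after 72 hours will have no Holter count; the report should say how many there are.
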